- To compare the genomic damage in both types of iron supplementation.

Study hypothesis

Weekly ferrous sulfate supplementation will be more effective in the prevention of IDA in infants than daily supplementation due to a higher adherence and a lower incidence of adverse effects. Weekly iron supplementation will cause less genomic instability as compared with daily iron supplementation.

Study design

Randomized controlled clinical trial.

Study sample

Eligibility

Infants performing monthly health controls at the Pediatric Health Observatory of IDIP, La Plata Children's Hospital, from birth to six months of age will be included in the study.

Inclusion, exclusion and elimination criteria

Inclusion criteria: Three-month-old clinically healthy breastfeeding infants with birth age > 37 weeks, birth weight between 2500 and 4000 g, a normal fetal and neonatal history, that attend IDIP's Health Observatory and whose parents/guardians express the will to participate in the study and sign a written informed consent form.

Exclusion criteria: Anemic and/or iron deficient infants or with chronic diseases or acute infections or under antibiotic/vitamin treatment within 15 days prior to the study.

Elimination criteria: infants with severe intolerance to iron preventive supplementation, who will receive the alternative preventive treatment with ferrous fumarate or iron polymaltose complex).

Unit of analysis: Three to six month-old infants.

Sample size and selection

According to ENNyS, the prevalence of anemia in 6-9 months old infants is 50.8%. Our controlled interventions would reduce such prevalence to 30%. Sample size was estimated with 0.95 significance level and 0.80 power, resulting in 174 infants (n= 87 for each supplementation group). This number was adjusted considering a 15% dropout, thus enrolling 204 infants.

Methods

Operational definition of variables

Main variables

-Anemia is defined as the “decrease in the total amount of blood cells or a blood hemoglobin (Hb) concentration more than 2 standard deviations below the mean of an age- and sex-matched reference range”. We will define the presence of anemia when Hb < 9.5 g/dL at 3 months of age and Hb < 11.0 g/dL at six months of age (CDC, 2007).

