- Genomic damage: DNA damage assessed by cytomolecular techniques using the Comet assay (damage index assessment in 200 cells, quantifying damage by Tail moment and Olive Tail moment). The frequency of oxidized DNA bases will be determined by competitive 8-oxo-dG Elisa.

Other variables:

- Sex, weeks of gestation, umbilical cord clamping.

- Infant nutritional condition will be assessed by anthropometry (weight, height, head circumference) at three and six months.

- Sociodemographic data of infants and relatives, including place of residence, unsatisfied basic needs, maternal education.

- Maternal nutritional condition will be evaluated with anthropometry and iron status.

- Environmental exposure to genotoxic agents (antibiotics, radiation (X-rays) and chemical substances like pesticides, solvents and industrial waste) will be assessed by questionnaire.

Data collection

-Patient enrolment

During health control visits to IDIP Health Observatory on the first and second month of life, parents and tutors will be invited to participate in the study; the study's protocol, its aims and benefits will be explained in a plain language. They will be asked to sign a written informed consent form in case they accept their children be incorporated to the study. Infants meeting the inclusion criteria with exclusively breastfeeding (EBF) will be randomly divided into three groups: weekly, daily and no supplementation. Those with mixed feeding (breastfeeding and formula; MF) will be randomly divided into two groups: weekly and daily supplementation.

- Intervention

Weekly supplementation (EBF or MF): infants will receive a weekly dose of ferrous sulfate (4mg/kg/week).

Daily supplementation (EBF or MF): infants will receive a daily dose of ferrous sulfate (1 mg/kg/day).

Without intervention (only EBF): infants will receive no supplementation, following the current SAP guidelines. Ferrous sulfate will be supplied by pediatricians.

- Randomization

Randomization will be performed by computer-generated random sequences of numbers in blocks of variable length. Randomization will be stratified by type of intake (EBF or MF).

Treatment assignments will be placed in sequentially numbered, opaque and sealed envelopes which will be consecutively put in a box and later removed one at a time. The person in charge of the random allocation process will not take part in the enrollment process.

- Blinding

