Pediatricians in charge of supplementation will know the assigned intervention only when the envelopes are open. Professionals in charge of performing laboratory tests will not know intervention assignments.

-Sample collection. Surveys

Before supplementation, 3-ml blood samples from infants will be drawn to assess anemia, ID, and genomic stability. All non-anemic/iron deficient infants will be recruited and will be supplemented

according to the group assigned during 12 weeks (three months). At the end of this period (six months of age), blood samples will be drawn again to measure the study variables. Infant and family sociodemographic data will be surveyed at the first visit (three months of age). Anthropometric measurements will be taken at three and six months. Nutritional assessment of the mothers will be performed at the beginning and at the end of the study, measuring weight and height and drawing blood samples for anemia and ID assessment.

- Intervention progress monitoring

Pediatricians will prescribe iron doses and manner of administration. Parents and/or tutors will receive one or more droppers with ferrous sulfate sufficient to complete one-month supplementation, considering that all infants will perform monthly health controls. The Telegram program “LactaPlusIDIPBOT”, designed at IDIP, will be used to send reminders for iron supplement intake. They will be also contacted weekly (Facebook messenger, Whatsapp, Telegram). To monitor adherence, we will use a daily/weekly consumption record form that will be completed by parents/tutors and delivered at each health control. To determine consumption, we will control de excess volume in droppers during each monthly control.

- Record of adverse effects

Parents and/or tutors will receive a form to register adverse effects which will be presented at each monthly control. They will register intake rejection, constipation, vomiting, diarrhea, and abdominal pain. Infants with intolerance to iron supplementation will be excluded from the study but will continue on an alternative treatment (1 mg/kg/day fumarate or iron polymaltose complex).

- Laboratory tests

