We will also determine the incidence of adverse effects and the incidence of low treatment adherence at six months of age for weekly vs. daily iron supplementation in both EBF and MF and calculate RR (95% CI) at six months of age.

[figure not shown]
Means and differences of enzymatic SOD and CAT activity and TBARS concentration at three and six months will be compared in both study groups. The same will apply to the Comet and 8 oxodG assays. Differences between groups will be determined by Anova or Kruskal-Wallis test for quantitative variables with post-hoc comparisons and Chi-square for categorical variables. Within group comparisons will be analyzed using Student's or Wilcoxon test.

Risk of bias assessment

Selection bias could be present since parents/tutors willing to participate could show higher interest in the research project than those who do not participate. Considering that the population sample attends for monthly controls, a trust relationship may be established between parent/tutor and pediatrician, resulting in a higher degree of adherence to supplementation than in the general population.

Project Schedule

Study flowchart

Work plan

SPECIFIC OBJECTIVE 1: Compare the effectiveness of weekly, daily and no iron supplementation in EBF infants.

SPECIFIC OBJECTIVE 2: Compare the effectiveness of weekly, daily and no iron supplementation in MF infants.

| ACTIVITY | RESPONSIBLE | EXPECTED RESULT |
|--|----------------------------|--|
| Enrollment of infants according to the inclusion criteria. | Pediatricians | Incorporate infants who comply with inclusion criteria |
| Informed consent. | | |
| Intervention assignment. | Statistician | Random allocation |
| Blood sample collection. | Laboratory technician | Adequate specimen collection (enough volume, non clotted) |
| Hemoglobin, ferritin, PCR and sTfR determinations. | Biochemists | Assessment of the prevalence of anemia and iron deficiency |
| Indication for and monitoring of the intervention | Pediatricians | Complete registry of the intervention. |
| Text message reminders | Pediatricians | Intervention adherence. |
| Weight and height measurement. | Pediatrician, Nutritionist | Determine the anthropometric nutritional condition. |
| Registry of data. | Data entry | Complete database. |
| Data analysis and interpretation of results. | Team, Statistician | Report of results and conclusions. |

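### The protocol does not fix whether infants are randomized before or after the 3-month blood test that decides eligibility, nor at which of these points the 204 are counted

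*Protocol*

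**What the plan says.** Five parts of the protocol bear on the order of testing and allocation.

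- **Inclusion, exclusion and elimination criteria.** Absence of anemia and iron deficiency is not among the inclusion criteria. Both conditions are exclusion criteria. Elimination covers only severe intolerance to the supplement.
- **Data collection, Patient enrolment.** Families are approached at the month 1 and month 2 visits and asked for consent. The same paragraph continues: "Infants meeting the inclusion criteria with exclusively breastfeeding (EBF) will be randomly divided into three groups: weekly, daily and no supplementation". Mixed-feeding infants are divided likewise into two groups. The paragraph mentions neither the exclusion criteria nor a laboratory result.
- **Sample collection. Surveys.** Blood is drawn before supplementation to assess anemia, iron deficiency and genomic stability. Then: "All non-anemic/iron deficient infants will be recruited and will be supplemented", in line with the assigned group.
- **Work plan, specific objectives 1 and 2.** The rows run: enrollment, consent, "Intervention assignment. | Statistician | Random allocation", blood collection, the hemoglobin, ferritin, CRP and sTfR determinations, then indication and monitoring of the intervention.
- **Sample size and selection.** The calculation is described as "resulting in 174 infants (n= 87 for each supplementation group"), followed by: "This number was adjusted considering a 15% dropout, thus enrolling 204 infants".

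Blinding says that the pediatricians learn the arm when the envelope is opened. It does not say what must be complete before an envelope may be opened.

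**The concern.** Whether eligibility is confirmed before or after allocation is a core procedure, and a site needs one answer. Patient enrolment and the Work plan table, read in order, give allocation first. Sample collection can be read as giving the test first.

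If a site allocates first, two things follow.

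1. Some randomized infants turn out to be anemic or iron deficient and leave before treatment. Data analysis promises intention-to-treat to handle changes of feeding type or arm, and separately says how losses to follow-up are treated. An infant who was never eligible is neither. Keeping such infants would put some who were already anemic into a comparison of anemia incidence. Removing them departs from the set as randomized. The protocol does not say which applies.
2. The step from 174 to 204 is for dropout only. Infants who fail the blood test would come out of the same 204.

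**Working it through.** **Reproducing the plan's figure.** Inputs from Sample size and selection: p1 = 0.508, p2 = 0.30, power 0.80, two equal groups. The stated 0.95 significance level is read as two-sided alpha 0.05, which reproduces the stated n.

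With pooled variance and no continuity correction, p̄ = (0.508 + 0.30)/2 = 0.404 and

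n = [1.960 × √(2 × 0.404 × 0.596) + 0.842 × √(0.508 × 0.492 + 0.30 × 0.70)]² / 0.208²

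= (1.360 + 0.571)² / 0.04326 = 86.2, rounded up to 87 per group and 174 in total.

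Dropout: 174 / 0.85 = 204.7, against the stated 204. The plan's figures therefore reproduce, apart from rounding down, and they leave no room for any loss other than the 15%.

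**If the 204 are counted before the test.** Let e be the share of randomized infants who fail the blood test. The protocol gives no value for e, so the rates below are assumptions. The 28.9% is the anemia prevalence that the Theoretical framework section reports for infants under 6 months. It is not a rate at 3 months with the 9.5 g/dL cut-off, and it does not count iron deficiency without anemia. It serves only as one point in a range.

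- Evaluable = 204 × (1 − e) × 0.85
- Power = Φ{[0.208 × √m − 1.360] / 0.678}, where m is half the evaluable number and 0.678 = √(0.508 × 0.492 + 0.30 × 0.70)
- Number to randomize to keep 174 evaluable = 174 / [0.85 × (1 − e)]

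| Assumed e | Eligible of 204 | Evaluable | Power | Number to randomize |
|---|---|---|---|---|
| 0% | 204 | 173 | 80% | 205 |
| 5% | 194 | 165 | 78% | 216 |
| 10% | 184 | 156 | 76% | 228 |
| 20% | 163 | 139 | 71% | 256 |
| 28.9% | 145 | 123 | 66% | 288 |

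Example for e = 28.9%: 204 × 0.711 × 0.85 = 123.3, so m = 61.6. Then (0.208 × 7.85 − 1.360) / 0.678 = 0.40, and Φ(0.40) ≈ 0.66.

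**If the 204 are counted after the test.** The 0% row applies: about 173 evaluable, 80% power, no change.

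The power figures use the plan's own comparison of two groups of 87. The actual layout, with three exclusively breastfed arms and two mixed-feeding arms, is a separate matter and is not assessed here.

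**The case against.** The strongest reply is that the Work plan table is not a timeline. Its columns are activity, responsible party and expected result, and nothing calls it chronological. It lists enrollment before consent. It places weight and height after the reminders, although anthropometry is also taken at 3 months, and it lists blood collection once although blood is drawn twice. The assignment row may cover only the statistician's preparation of the sequence. The reference to inclusion criteria in Patient enrolment may be shorthand for eligible. Sample collection has infants recruited once tested. The study flowchart, where the order might be drawn, is not shown in the copy at hand.

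Much of this stands. A reader might infer that infants will in fact be randomized and then dropped, and that the 204 cannot be the infants analyzed. The documents do not establish either. A reader might also infer that pediatricians who know the arm could influence exclusions. No section puts envelope opening ahead of the results or describes such a route, so that is speculation and forms no part of this point. The blood test is taken before treatment and the laboratory is blinded, so exclusion on its result mainly costs numbers and does little to bias the comparison.

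The reply does not settle the order. Patient enrolment goes from consent straight to random division on the inclusion criteria, and no text at hand puts allocation after the laboratory result. The word for recruitment in Sample collection makes that section pull against the other two without resolving the question.

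**Conclusion.** The point holds as an unresolved conflict on a core step, and it should be corrected. Patient enrolment and the row order of the Work plan put allocation before the eligibility test, while Sample collection can be read the other way.

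The cost depends on which reading is followed. With allocation first and assumed failure rates of 5% to 28.9%, between 165 and 123 infants are evaluable instead of 174, power is between 78% and 66%, and the intention-to-treat set is undefined for the infants excluded. With the 204 counted after the test, nothing is lost. These figures rest on the plan's own event rates, its 15% dropout, its two-group framing and failure rates that the protocol does not supply. They show what is at stake under one reading and do not predict a shortfall.

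**What to change.** - In Patient enrolment, Randomization and Sample collection, state that the next sealed envelope is opened only after the 3-month hemoglobin, ferritin, CRP and sTfR results and all exclusion criteria have been checked and eligibility has been recorded.
- Reorder the Work plan table so that intervention assignment follows the laboratory determinations, and make sure the flowchart agrees.
- In Sample size and selection, state that the 204 are infants randomized after passing the screen. If allocation before the test is intended, restate the evaluable number and power with an explicit screen-failure allowance, and say in Data analysis how randomized infants who fail the test are handled.

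The cost is small. The sample is already drawn before supplementation, so no new test or staff are needed. There is a short wait for results between blood draw and allocation. Some consented infants will never be randomized, so more must be approached to reach 204. If screening first was always the intention, the change only confirms it.
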